4.1.3 Target volume delineation

4.1.3.1 Gross tumor volume (GTV)

The primary gross tumor volume (GTVp) will be contoured on the planning CT using radiographic and clinical information to define its extent. Image registration of staging scans including diagnostic CT, PET/CT, and/or MRI as available to aid delineation of GTVp is recommended, but not mandatory.

The nodal gross tumor volume (GTVn) will be contoured on the planning CT using radiographic and clinical information. Nodes meeting the criteria below will be considered positive and included in GTVn:

- Max SUV greater 3.0
- The short-axis diameter is ≥ 1.5 cm (level II), ≥ 1.0 cm (level I, III, IV, and V), or ≥ 0.8 cm (retropharyngeal)
- The node shows central necrosis

Suspicious nodes will be defined as those that do not meet the above criteria, but satisfy any of the criteria below:

- The combined diameter of the lymph node ≥ 17 mm on axial imaging
- FDG uptake greater than the adjacent blood pool
- Any size retropharyngeal node
- Heterogeneous enhancement or rounded appearance

At the discretion of the treating radiation oncologist, suspicious nodes can be included either as part of GTVn or included in CTVn as discussed below.

4.1.3.2 Clinical target volume (CTV)

CTVSR

GTVp will be expanded by 5 mm to create CTVp. CTVp may be expanded further to include surrounding anatomic structures at risk for microscopic spread such as the adjacent soft palate or glossotonsillar sulcus for tonsil cancers or the adjacent contralateral base of tongue for base of tongue cancers at the discretion of the treating radiation oncologist. CTVp should exclude structures that are a natural barrier to spread (e.g. bone).

CTVn will include the following:

-Bilateral level II

- Except in well-lateralized tonsil cancers (defined as having no invasion of the base of tongue and minimal invasion of the soft palate with >1 cm distance from the uvula), where the node negative contralateral level II may be omitted

- In the node positive neck, cranial extent of level II will be the base of skull

- In the node negative neck, cranial extent of level II will be the transverse process of C1 vertebrae or where the posterior belly of the digastric muscle crosses over the jugular vein

- Nodal level(s) with an involved node (i.e. GTVn)

- Nodal level(s) immediately adjacent to involved node (e.g. if level II has an involved node, levels III is included)

- Nodal level(s) with suspicious nodes

- Ipsilateral lateral retropharyngeal nodal region

- Level V is included if there are 2 or more involved nodal levels in the ipsilateral neck

- Level IB is included only if it harbors an involved or suspicious node

4.1.3.3 Planning target volume (PTV)

GTVp and GTVn will be expanded by 5 mm in all directions to create PTVHR.

CTVp will be expanded by 5 mm in all directions to create PTVp. CTVn will be expanded by 3 mm in all directions to create PTVn. PTVp and PTVn will be combined to create PTVSR.

 4.1.4 Treatment planning

Radiotherapy must be delivered using IMRT. IMRT may be implemented using any delivery platform, including volumetric modulated arc therapy (VMAT), step and shoot IMRT, or helical tomotherapy.

 4.1.4.1 Coverage constraints

Target volume	Per protocol	Acceptable variation (Minor deviation)	Major deviation
PTVHR	
 -At least 95% of the PTV should be covered by the prescription dose -At least 99% of the PTV should receive 93% of the prescription dose -Dose should not exceed 107% of prescription dose 	
 -None -At least 97% of the PTV should receive 93% of the prescription dose -Dose should not exceed 110% of prescription dose 	
 -<95% of the PTV is covered by the prescription dose -<97% of the PTV receives 93% of the prescription dose -Maximum dose is >110% of prescription dose
PTVSR	
 -At least 95% of the PTV should be covered by the prescription dose 	
 -At least 93% of the PTV should be covered by the prescription dose 	
 -<93% of the PTV is covered by the prescription dose

 4.1.4.2 Organ at risk (OAR) constraints
12 fractions

Mandatory:

Organ	Per protocol	Acceptable variation (Minor deviation)	Major deviation
Spinal cord	Max < 34 Gy	None	Max ≥ 34 Gy
Spinal cord + 5 mm	Max < 38 Gy	Max < 41 Gy	Max ≥ 41 Gy
Brainstem	Max < 38 Gy	Max < 41 Gy	Max ≥ 41 Gy
Brainstem + 5 mm	Max < 44 Gy	None	Max ≥ 44 Gy
Mandible	Max < 46.6 Gy	Max < 48.8 Gy	Max ≥ 48.8 Gy

Recommended:

Contralateral parotid: mean < 16-21 Gy
 Contralateral submandibular gland: mean < 22-27 Gy
 Cochlea: maximum < 28-34 Gy, mean < 23-28 Gy
 Oral cavity (excluding PTV): mean < 16-20 Gy
 Constrictors: mean < 29-34 Gy
 Post-arytenoid and cricoid space: mean < 19-24 Gy
 Larynx: mean < 22-27 Gy
 Cervical esophagus: mean < 16-20 Gy
 Brachial plexus: max < 44-47 Gy
 Brain: max < 44 Gy

15 fractions

Mandatory:

Organ	Per protocol	Acceptable variation (Minor deviation)	Major deviation
Spinal cord	Max < 37 Gy	None	Max ≥ 37 Gy
Spinal cord + 5 mm	Max < 43 Gy	Max < 44 Gy	Max ≥ 44 Gy
Brainstem	Max < 43 Gy	Max < 44 Gy	Max ≥ 44 Gy
Brainstem + 5 mm	Max < 48 Gy	None	Max ≥ 48 Gy
Mandible	Max < 48.9 Gy	Max < 51.5 Gy	Max ≥ 51.5 Gy

Recommended:

Contralateral parotid: mean < 17-22 Gy
 Contralateral submandibular gland: mean < 23-29 Gy
 Cochlea: maximum < 30-37 Gy, mean < 25-30 Gy
 Oral cavity (excluding PTV): mean < 17-21 Gy
 Constrictors: mean < 30-37 Gy
 Post-arytenoid and cricoid space: mean < 20-25 Gy
 Larynx: mean < 23-29 Gy
 Cervical esophagus: mean < 17-21 Gy
 Brachial plexus: max < 46-49 Gy
 Brain: max < 46 Gy

20 fractions

Mandatory:

Organ	Per protocol	Acceptable variation (Minor deviation)	Major deviation
Spinal cord	Max < 40 Gy	None	Max ≥ 40 Gy
Spinal cord + 5 mm	Max < 46 Gy	Max < 49 Gy	Max ≥ 49 Gy
Brainstem	Max < 46 Gy	Max < 50 Gy	Max ≥ 50 Gy
Brainstem + 5 mm	Max < 52 Gy	None	Max ≥ 52 Gy
Mandible	Max < 54.6 Gy	Max < 57.2 Gy	Max ≥ 57.2 Gy

Recommended:

Contralateral parotid: mean < 19-23 Gy
 Contralateral submandibular gland⁺: mean < 26-30 Gy
 Cochlea: maximum < 33-40 Gy, mean < 27-32 Gy
 Oral cavity (excluding PTV): mean < 19-22 Gy
 Constrictors: mean < 33-40 Gy
 Post-arytenoid and cricoid space: mean < 22-26 Gy
 Larynx: mean < 26-30 Gy
 Cervical esophagus: mean < 19-22 Gy
 Brachial plexus: max < 52-54 Gy
 Brain: max < 52 Gy

4.1.4.3 Treatment delivery

All patients will receive one fraction per day, 5 days per week (except at dose level 1, where patients will receive one fraction per day, 4 days per week). Patients who miss more than 1 planned treatment (or encounter more than 1 holiday during treatment) should attempt to make up the missed day(s) with a second daily fraction more than 6 hours apart. Daily cone-beam CT (CBCT) must be used for patient set-up (image-guided RT). Patients will preferentially start RT on a Monday, but this is not mandatory.

Total elapsed days

	Per protocol	Acceptable variation (Minor deviation)	Major deviation
12 fractions	18-20	21-25	>25
15 fractions	18-21	22-26	>26
20 fractions	26-28	29-33	>33
30 fractions	40-42	43-47	>47

4.1.4.4 Re-planning

If a patient loses a significant amount of weight on treatment, or the tumor contour changes substantially, repeat CT simulation and planning is allowed.

4.2 Toxities and Dosing Delays/Dose Modifications

Any subject who receives treatment on this protocol will be evaluable for toxicity. Each patient will be assessed for the development of toxicity according to the Time and Events table in section 5.4. Toxicity will be assessed according to the NCI Common Toxicity Criteria for Adverse Events (CTCAE), version 5.0.

The dose constraints for radiation therapy are described in sections 4.1.4.2. No alterations in treatment doses are allowable per protocol.

4.3 Concomitant Medications/Treatments

Supportive medications may be given at any point during the treatment course at the discretion of the treating physicians. These medications include:

- Anti-emetics
- Non-opiate and opiate pain medications
- Antidiarrheals
- Nutritional supplementation
- Anti-depressants

4.4 Other Modalities or Procedures

4.4.1 Concurrent systemic therapy

Concurrent systemic therapy will be administered using weekly cisplatin of 40 mg/m². Dose modifications should be performed per the standard of care at the treating facility. Patients are recommended to receive concurrent weekly cisplatin as long as it is tolerated as determined by the treating medical oncologist. Details of the systemic therapy can be found in section 8.0.

4.4.2 Gastric tubes

Gastrostomy tubes (feeding tubes) are optional for patients on this study. Physicians should attempt to avoid gastrostomy if patients are receiving ipsilateral radiotherapy. However, gastrostomy tubes are strongly recommended in the following scenarios:

- More than 10% body weight loss prior to diagnosis (prophylactic)
- Baseline BMI < 25 (prophylactic)
- More than 10% body weight loss on treatment (reactive)

The gastrostomy tube should be removed after patients maintain a stable or increasing weight for 1-2 weeks without enteral supplementation (or as clinically indicated).

4.4.3 Speech language pathology

Patients are strongly recommended to have evaluation and ongoing therapy as appropriate by a speech language pathologist before, during, and after radiation therapy.

4.5 Duration of Therapy

Duration of therapy will be per the treatment schedule as outlined in section 4.1.2 (3-4 weeks depending on the dose level).

Protocol therapy will end under the following conditions:

- Disease progression
- Inter-current illness that prevents further administration of treatment
- Unacceptable adverse event(s)

- Subject decides to withdraw from the study, OR
- General or specific changes in the patient's condition render the subject unacceptable for further treatment in the judgment of the investigator.

4.5.1 Subject Withdrawal

In the event a subject chooses to withdraw from the study, document if the is withdrawing from treatment only (and willing to be included in follow-up data collection), or if they are withdrawing from all study participation. For subject safety, the subject should be encouraged to return for a follow-up visit per the Time and Events Table in section 5.4.

Notify the Principal Investigator/Sponsor-Investigator and document the reason for withdrawal from study and the date of discontinuation.

4.6 **Duration of Follow Up**

Patients will be followed for 1 year from the completion of treatment according to the Time and Events table in section 5.4.

4.7 **Removal of Subjects from Protocol Therapy**

Subjects will be removed from therapy when any of the criteria listed in section 5.5 apply. Notify the Principal Investigator (or the co-Investigators if not available) and document the reason for treatment discontinuation and the date of discontinuation. The subject should be followed-up per protocol.

4.8 **Subject Replacement**

Subjects may be replaced in the study if they do not complete RT for reasons not related to toxicities associated with treatment. Because inadequate receipt of treatment may lead to a spuriously high rate of recurrence and/or inaccurate assessment of treatment side effects, these patients may be replaced. Patient replacement must be verified through review of the case by the Principal Investigator (or the co-Investigators if Principal Investigator is not available).

5.0 STUDY PROCEDURES

5.1 **Screening/Baseline Procedures**

Assessments performed exclusively to determine eligibility for this study will be done only after obtaining informed consent. Assessments performed for clinical indications (not exclusively to determine study eligibility) may be used for baseline values even if the studies were done before informed consent was obtained.

All screening procedures must be performed within 30 days prior to registration into the study unless otherwise stated. The screening procedures include:

5.1.1 Informed Consent

5.1.2 Medical history

- Complete medical and surgical history

5.1.3 Demographics

- Age, gender, race

- 5.1.4 Review subject eligibility criteria
- 5.1.5 Review previous and concomitant medications
- 5.1.6 Physical exam including vital signs
 - Temperature, pulse, blood pressure
- 5.1.7 Performance status
 - ECOG Performance status (0-2) or Karnofsky Performance Status (50-100)
- 5.1.8 Adverse event assessment
 - Baseline adverse events will be assessed pre-treatment using CTCAE v5.0. See section 7.2 for adverse event monitoring and reporting.
- 5.1.9 Pregnancy test (for females of child bearing potential)
 - See section 3.1.5.1 for definition
- 5.1.10 Completion of PRO instruments (before start of radiation treatment)
 - MDADI
 - UW-QOL
 - EQ-5D-5L
- 5.1.11 Feeding tube dependence assessment
 - See section 2.3.2 for definition
- 5.1.12 Standard lab work including creatinine
 - Assessment for cisplatin eligibility per medical oncologist

5.2 Procedures During Treatment

Dose escalation phase:

During each week of radiotherapy, following will be evaluated:

- Vital signs
- Physical exam
- ECOG performance status or Karnofsky performance status
- Adverse events assessment using CTCAE v5.0

Dose expansion phase:

Weekly visits will be conducted by the care team as per standard of care and not as part of trial procedures.

5.3 Follow-up Procedures

Patients will be assessed by a radiation oncologist and/or advanced practice provider at 1 month (+/- 1 week) and 3 months (+/- 2 weeks) from the completion of treatment per Time and Events Table (Section 5.4). More frequent visits are encouraged if the patient requires additional help with recovery and rehabilitation. Restaging PET/CT must be performed between 12-14 weeks from the completion of treatment.

Patients with a clinical complete response (cCR) based on history and physical exam and restaging PET/CT at 12-14 weeks as defined in Section 6.1.1 will undergo routine surveillance. Patients with less than cCR in the primary site will undergo directed biopsy of suspected site(s), and if positive, proceed with salvage transoral robotic surgery

(TORS). Patients with less than cCR in the neck will undergo neck dissection, with the extent of the neck dissection to be determined by surgeon discretion.

Patients with pathologically confirmed viable residual primary disease will be considered to have locoregional failure. Since the viability of residual nodal disease on pathology is often questionable at this time point (12-14 weeks post-treatment), and because adjuvant neck dissection is typically considered part of the original treatment package, residual nodal disease at neck dissection will not be considered a locoregional failure.

Patients will then be seen at 6 and 12 months (+/- 4 weeks) from the completion of treatment per Time and Events Table (Section 5.4). Patients with pathologically confirmed recurrent disease following assessment at these times points will be considered to have locoregional failure/recurrence. Subsequent and intervening follow-up visits will be made per physician preference.

5.4 Time and Events Table

Procedures/ Times	Pre-treatment	Weekly during treatment ^a	1 ^b , 3 ^c , 6 ^d , 12 ^d months post treatment
History and PE	X ^e	X	X
Performance status (ECOG/ KPS)	X ^e	X	X
AE assessment	X ^f	X	X
DLT assessment (only during dose escalation phase)		X	X
Patient reported outcomes (MDADI, UW-QOL, EQ-5D-5L)	X ^f		X
Feeding tube dependence assessment	X ^g		X
Pregnancy test	X ^h		
Lab work (creatinine)	X		
Restaging PET/CT			X ⁱ

^a Only during the dose escalation phase

^b +/- 1 week

^c +/- 2 weeks

^d +/- 4 weeks

^e ≤ 30 days prior to registration

^f Prior to initiation of RT

^g At the time of radiation oncology consultation

^h Urine or serum in applicable female within 2 weeks of registration

ⁱ At 12-14 weeks post RT only

5.5 Removal of Subjects from Study

Subjects can be taken off the study treatment and/or study at any time at their own request, or they may be withdrawn at the discretion of the investigator for safety, behavioral or administrative reasons. The reason(s) for discontinuation will be documented and may include:

5.5.1 Subject voluntarily withdraws from treatment (follow-up permitted)

5.5.2 Subject withdraws consent (termination of treatment and follow-up, see section 4.5.1)

- 5.5.3 Subject is unable to comply with protocol requirements
- 5.5.4 Subject demonstrates disease progression, however, continued treatment with study drug/treatment is permissible at the discretion of the investigator
- 5.5.5 Subject experiences toxicity that makes continuation in the protocol unsafe
- 5.5.6 Treating physician determines continuation on the study would not be in the subject's best interest
- 5.5.7 Subject becomes pregnant (pregnancy to be reported along same timelines as a serious adverse event)
- 5.5.8 Development of second malignancy (except for basal cell carcinoma or squamous cell carcinoma of the skin) that requires treatment, which would interfere with this study
- 5.5.9 Lost to follow-up. If a research subject cannot be located to document survival after a period of one year, the subject may be considered "lost to follow-up." All attempts to contact the subject during the one year must be documented.

6.0 MEASUREMENT OF EFFECT

6.1 Antitumor Effect

6.1.1 Definitions

Evaluable for toxicity: All subjects will be evaluable for toxicity from the time of their first treatment with radiotherapy.

Clinical complete response (cCR): Disappearance of all lesions on physical/clinical exam and negative PET/CT (12-14 weeks post-treatment), defined as no focal FDG avidity at the primary site (i.e. may have diffuse avidity consistent with post-radiation inflammation) and no focal FDG avidity above blood pool or liver of treated pathological lymph nodes per the Hopkins criteria (24). There can be no appearance of new lesions.

Locoregional recurrence (LRR): Biopsy-proven viable cancer originating from the primary tumor site (i.e. oropharynx) or a lymph node basin above the clavicles.

Locoregional control (LRC): Freedom from locoregional recurrence

Distant metastasis (DM): Recurrent cancer below the clavicles. Biopsy is strongly recommended but not mandated. If biopsy is not obtained, the initiation of anti-cancer therapy is assumed to indicate metastasis, with the date of scan prompting therapy serving as the date of metastasis.

Progression: locoregional recurrence or distant metastasis

Progression-free survival (PFS): Duration of time from start of treatment to time of progression or death.

Overall survival (OS): Duration of time from start of treatment to time of death.

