7.5 Stopping Rules

The primary hypothesis of the phase 1 study is that de-intensified HFRT is safe and tolerable. The trial will terminate during the rolling 6 dose escalation phase if it has reached level -1 and 2 patients experience dose limiting toxicity (DLT) at this dose level.

The secondary hypothesis is that the crude 1-year LRC rate is at least 85% (based on historical controls). In other words, for the target of 20 evaluable patients at 1 year, up to 3

patients can have a LRR and satisfy the pre-specified hypothesis. Thus, if a 4th patient enrolled on the trial experiences LRR within 1 year of completing the study treatment, the trial will be terminated for futility.

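### A locoregional recurrence suspected after the 12-14 week evaluation and never sampled for pathology is scored as controlled, because section 6.1.1 gives distant metastasis a no-biopsy rule but gives locoregional recurrence none

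*Combined protocol and SAP*

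**What the plan says.** Section 6.1.1 defines LRR as "Biopsy-proven viable cancer originating from the primary tumor site (i.e. oropharynx) or a lymph node basin above the clavicles" and LRC as "Freedom from locoregional recurrence". DM is defined differently: "Recurrent cancer below the clavicles. Biopsy is strongly recommended but not mandated". It also has a fallback, "If biopsy is not obtained, the initiation of anti-cancer therapy is assumed to indicate metastasis", with the event dated to the scan that prompted therapy. The composite is "Progression: locoregional recurrence or distant metastasis", and PFS adds death.

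Section 5.3 also relies on pathology. At 12-14 weeks, less than a clinical complete response (cCR) at the primary site leads to a directed biopsy, and less than cCR in the neck leads to neck dissection. Residual nodal disease found at that dissection is expressly not a locoregional failure. For the 6- and 12-month visits the rule is "Patients with pathologically confirmed recurrent disease following assessment at these times points will be considered to have locoregional failure/recurrence".

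Section 7.5 sets a secondary hypothesis of crude 1-year LRC of at least 85%. It allows up to 3 LRRs among 20 evaluable patients and stops the trial for futility "if a 4th patient enrolled on the trial experiences LRR within 1 year of completing the study treatment". Section 9.3.2.1 estimates LRC by cumulative incidence with death as a competing risk. Section 9.3.2.2 estimates PFS by Kaplan-Meier. Both point to section 6.2 for definitions, but 6.2 covers safety, so 6.1.1 is the operative text.

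**The concern.** The plan foresees that a recurrence may be treated without a biopsy and writes an event rule and a date for it, but only below the clavicles. Above the clavicles the same situation produces no event. No section requires a biopsy when locoregional recurrence is suspected after the 12-14 week evaluation, and none says how to score the patient if tissue is not obtained.

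A patient with evident late locoregional progression who starts non-surgical therapy without a biopsy therefore stays in the controlled group when the plan is followed exactly. This goes beyond a missing detail, because the stated rule assigns that patient the wrong outcome. The error can only remove failures. It favours a de-intensified regimen on LRC and PFS, and it can delay or prevent a futility stop that turns on a single patient.

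**Working it through.** **1. The plan's own figures.** Section 9.2 plans for 20 evaluable patients with 15% attrition: 20 / (1 - 0.15) = 23.5, rounded up to 24, and 24 × 0.85 = 20.4 evaluable. Section 7.5: 1 - 3/20 = 85%, and a 4th LRR gives 1 - 4/20 = 80%. Both reproduce.

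**2. How the definitions score one patient.** Take a recurrence suspected after the 12-14 week evaluation, treated non-surgically or fatal, with no tissue ever obtained.

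| Analysis | Scoring under the present text |
|---|---|
| LRR / LRC | No LRR; controlled |
| LRC, if the patient then dies | Competing event, not a locoregional failure |
| PFS | No event until DM or death, if either follows |
| Section 7.5 count | Not counted |

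The DM fallback does not properly cover this patient, because DM is limited to disease below the clavicles. Read loosely, its treatment-initiation wording would supply a PFS event but still leave LRC scored as controlled.

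**3. Effect at the threshold.** With exactly 4 true failures among 20, one of them unbiopsied, the count is 3/20. LRC then reads 85% (hypothesis met, no stop) instead of 80% (stop). Each missed failure moves crude LRC by 1/20 = 5 points.

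**4. Effect without fixing the number of failures.** Let q be the true 1-year locoregional failure rate and u the share of failures never confirmed by pathology. Neither is in the documents, so both are assumptions. The counted failures are Binomial(20, q(1 - u)), and the quantity of interest is P(X ≥ 4).

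| q | u = 0 | u = 5% | u = 10% | Fall at 5% | Fall at 10% |
|---|---|---|---|---|---|
| 10% | 0.133 | 0.116 | 0.099 | 1.7 points | 3.4 points |
| 15% | 0.352 | 0.316 | 0.281 | 3.6 points | 7.2 points |
| 20% | 0.589 | 0.544 | 0.497 | 4.5 points | 9.1 points |
| 25% | 0.775 | 0.735 | 0.690 | 4.0 points | 8.5 points |

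The fall is about 2-5 points at u = 5% and 3-9 points at u = 10%. At u = 25% it would be 7.5-24 points, but nothing in the documents suggests a share that high.

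**5. How often the threshold case in step 3 arises.** Exactly 4 failures in 20 has probability 0.09, 0.18, 0.22 and 0.19 at q = 10%, 15%, 20% and 25%.

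**The case against.** The strongest defence is that requiring pathology is deliberate. Section 6.1.1 accepts diffuse post-radiation avidity within cCR, and section 5.3 says that the viability of residual nodal disease at 12-14 weeks is often questionable. Pathological confirmation is applied consistently across 5.3, 6.1.1 and 6.1.2 and guards against false-positive failures. That rationale stands. It supports letting pathology decide when it exists, but it does not explain why a recurrence with no pathology should count as control.

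The exposed group is also narrow, and this stands too. Less than cCR at 12-14 weeks already triggers biopsy or neck dissection, and surgical salvage yields tissue. A reader might infer that any unbiopsied locoregional failure is lost for good and stays progression-free until death. The documents do not support that. Tissue obtained later would still make it an LRR, and a later DM ends progression-free status as well as death does.

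A reader might also take the chance that at least one of 4 recurrences is missed, 1 - (1 - u)^4 = 19%, 34% or 68% at u = 5%, 10% or 25%, as the size of the problem. Those figures presuppose exactly 4 true recurrences and an assumed share. The unconditional falls in the working are the fairer measure. The 80%/85% contrast also assumes a denominator of exactly 20, whereas the section 7.5 count covers any enrolled patient, up to 24.

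Finally, LRC and PFS are secondary endpoints. The primary endpoint, the MTD, is not affected.

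**Conclusion.** The point holds for late locoregional recurrences (suspected after the 12-14 week evaluation) that are treated non-surgically, or are fatal, without tissue ever being obtained. For these, following the plan exactly biases LRC, PFS and the section 7.5 count toward a better result.

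The direction is certain and the size is not. It depends on u and q, which the documents do not give, and it may be small if biopsy is near-universal. On the assumptions stated, it is a fall of about 2-5 points (u = 5%) or 3-9 points (u = 10%) in the chance of reaching a 4th counted LRR. It is worth correcting because one patient can decide both the hypothesis and the stop, and because a rule written in advance avoids case-by-case adjudication of that patient.

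**What to change.** Change the endpoint scoring only. Add to the LRR definition in section 6.1.1:

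> If no pathology is obtained for a locoregional recurrence suspected after the 12-14 week evaluation, initiation of anti-cancer therapy for it, or death with documented locoregional progression, counts as LRR, dated to the scan or exam that first showed it. Where pathology is obtained, including from a surgical specimen, pathology decides. Neck dissection for less than cCR at 12-14 weeks is not an LRR (section 5.3).

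The last two sentences are needed. Without them, a protocol-directed neck dissection done without a prior biopsy could count as an LRR, which would contradict section 5.3 and could feed a false futility stop.

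Align the 6- and 12-month sentence in section 5.3, state that the section 7.5 count uses this definition, and report biopsy-proven-only LRC and PFS as a sensitivity analysis.

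The cost is a few sentences. No procedures are added, and the sample size of 24 and the 3-of-20 threshold are unchanged. The downside is an occasional false-positive LRR. The sensitivity analysis would make it visible but could not reverse a stop already triggered.
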